### 9.3.3. Analysis of Key Secondary Endpoints

The analyses for key secondary endpoints as in Section 3 will be performed for both the “treatment regimen” and “efficacy” estimand as described in Section 9.3.1 using the graphical testing scheme. The details of graphical testing scheme will be described in the SAP.

The analysis of the hierarchical combination PRO endpoint will be performed with the Finkelstein-Schoenfeld method, and the win ratio (Pocock et al. 2012) will be reported as the measure of treatment effect.

The last measurement prior to randomization for all three PRO endpoints will be used as baseline. For the “treatment regimen” estimand, missing values at Week 52 will be imputed through multiple imputations based on the reason of missingness as described in Section 9.3.1.

Analysis of percent change in AHI, percent change from baseline in body weight, CRP at the 52-week visit and change in SBP at the 48-week visit will be conducted in a manner similar to the primary efficacy analyses with baseline AHI stratum added in the model, and baseline of the corresponding variable as a covariate. Analysis of percent change in AHI will not include the baseline AHI stratum.

Comparisons at the 52-week visit between the treatments relative to the proportion of participants achieving  $\geq 50\%$  AHI reduction and  $AHI < 5$  or ( $AHI \geq 5$  and  $AHI \leq 14$  and  $ESS \leq 10$ ) will be conducted using logistic regression analysis including terms for treatment, pooled country, gender, and baseline AHI as a covariate.

Analysis aligned to each estimand will be evaluated at the full significance level of 0.05 contingent on reaching statistical significance of the primary objective.

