| SS | 1.2) Treatment-Emergent Abnormal Laboratory Results ^a and Vital Signs | For laboratory results, baseline period is defined as prior to the first dose time and will include all scheduled and unscheduled measurements. If the first dose time is missing, then any data collected on the date of the first dose will be treated as baseline. For vital signs, baseline period is defined as measurements collected prior to the first dose. | Postbaseline will be defined as after the baseline period through the end of the study participation. All scheduled and unscheduled measurements will be included. |

| Analysis Set | Analysis Type | Baseline | Postbaseline |
|--------------|---|---|---|
| | | If the first dose date is missing, then the randomization date will be used instead of first dose date. | |
| SS | 1.3) Change from Baseline for Laboratory Results ^a , and Vital Signs | The last scheduled and unscheduled nonmissing assessment recorded during the baseline period defined above (1.2). | Postbaseline will be defined as above (1.2). Only scheduled visits will be included. The ED visits are considered scheduled visits. |

Abbreviations: ED = early discontinuation; SS = Safety Analysis Set.

^a Immunogenicity related analysis is specified in Section [4.6.3.5](#).

For AHI analyses, baseline is defined as the last nonmissing measurement prior to the first dose.

The following paragraphs define selection of the PRO response which will be used for analysis at baseline and postbaseline visits. To select the baseline observation for PROs which are planned to be completed on the same day as the PSG (ESS, FOSQ, PROMIS, PGIS, SF-36v2 acute form, and EQ-5D-5L), the observation completed on the day or on the next day of the start of the baseline PSG will be selected. If multiple responses are completed within this period, the last response given within this timeframe will be selected. If no response was provided within this timeframe, the latest observation completed prior to the first dose will be selected. If a baseline still cannot be identified, the earliest observation within a 7-day window from the start of treatment date will be selected.

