4.1.1. Adjustment for Covariates

The study is stratified by country/geographic region, OSA severity (not severe [AHI <30], severe [AHI \geq 30]), and gender. Unless otherwise specified, the following factors will be adjusted for: geographic region (US/OUS), OSA severity (not severe [AHI <30], severe [AHI \geq 30]), and gender. The value for stratification factors will be obtained from the data collected or derived from the eCRF or PSG results. In addition, the baseline value of the endpoint will be used as a covariate when appropriate.

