4.4. Secondary Endpoints Analysis

4.4.1. Key Secondary Endpoints

A graphical approach for multiple comparisons will be used to strongly control the overall Type 1 error (2-sided alpha level of 0.05) for testing the superior treatment effect of tirzepatide MTD over placebo including the key secondary endpoints as listed below.

- percent change in AHI at Week 52
- percent of participants with $\geq 50\%$ AHI reduction at Week 52
- percent of participants at Week 52 with
 - AHI <5 or
 - (AHI 5 through 14 and ESS ≤ 10)
- percent change from baseline to Week 52 in body weight
- change from baseline to Week 48 in SBP
- change from baseline to Week 52 in C-reactive protein (high-sensitivity C-reactive protein)
- change in sleep apnea-specific hypoxic burden (% minutes/hour)
- change in PROMIS Sleep-related impairment short form 8a, and
- change in PROMIS Sleep disturbance short form 8b.

Analytical approaches for the hierarchical assessment of PROs are described in Section 4.4.3.1 and a summary of the analysis approach for all other key secondary endpoints is provided in Section 4.4.1.1.

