4.4.1.1. Main Analytical Approaches

Analysis of percent change in AHI, percent change from baseline to Week 52 in body weight, change from baseline to Week 52 in log of high-sensitivity C-reactive protein, change from baseline to Week 48 in SBP, change from baseline to Week 52 in PROMIS Sleep-related impairment, change from baseline to Week 52 in PROMIS Sleep disturbance, and change from baseline to Week 52 in log of hypoxic burden will be conducted in a manner similar to the primary efficacy analyses using an ANCOVA model with treatment, strata (geographic region [US/OUS], AHI stratum [not severe (AHI <30), severe (AHI \geq 30)], and gender), and baseline of the corresponding variable as a covariate for the treatment regimen estimand. If the hypoxic burden is reported to be 0, log (1) will be used in place of the log of hypoxic burden. The analysis method utilizing data from both ISAs for change from baseline to Week 52 in PROMIS sleep Impairment and PROMIS Sleep disturbance is described in the integrated efficacy analysis plan.

For the efficacy estimand, the MMRM analyses will be conducted as described in Section 4.1. For both estimands, analysis of percent change in AHI will adjust for the continuous, fixed baseline value of AHI instead of the baseline AHI stratum (not severe, severe).

Comparisons at the 52-week visit between the treatments relative to the proportion of participants achieving \geq 50% AHI reduction and AHI <5 or (AHI 5 through 14 and ESS \leq 10) will be conducted using logistic regression analysis including the following terms as a covariate:

- treatment
- geographic region (US/OUS)
- baseline AHI, and
- gender.

Unconditional risk differences will also be provided for these endpoints using logistic regression (Ye et al. 2023).

Analysis aligned to each estimand will be evaluated at the full significance level of 0.05 contingent on reaching statistical significance of the primary objective.

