4.4.3. Supportive Secondary Endpoints

Unless otherwise specified, all supportive/other secondary efficacy analyses will be guided by the “efficacy” estimand and will be conducted using the EAS. Missing data will be handled using an MMRM.

Table GPIF.4.3. Secondary Measures Not Controlled for Type 1 Error

| Objective – Demonstrate Superiority of Tirzepatide MTD to Placebo for: | Endpoint | Analytical Approaches |
|--|--|---|
| Change in excessive daytime sleepiness | Change in ESS score from baseline to Week 52 | MMRM analysis described in Section 4.4.1.1 will be conducted. |

| Objective – Demonstrate Superiority of Tirzepatide MTD to Placebo for: | Endpoint | Analytical Approaches |
|---|---|---|
| Change in patient-reported functional status as assessed by FOSQ (10 items) | Change in FOSQ-10 total score from baseline to Week 52 | MMRM analysis described in Section 4.4.1.1 will be conducted. |
| Change in patient-reported functional status as assessed by FOSQ (30 items) | Change in FOSQ (30 item) total score and all functional domain scores from baseline to Week 52 | MMRM analysis described in Section 4.4.1.1 will be conducted. |
| Change in Body Weight | Percent of participants who achieve $\geq 10\%$, $\geq 15\%$, and $\geq 20\%$ body weight reduction. | Logistic models described in Section 4.4.1.1 with the following covariates: treatment, geographic region (US/OUS), baseline AHI (not severe/severe), gender, and baseline bodyweight as a covariate. |
| Change in Lipid Parameters | Change in: HDL-cholesterol non-HDL-cholesterol triglycerides | MMRM analysis described in Section 4.4.1.1 will be conducted. |
| Hierarchical assessment of PRO change | A hierarchical combination of the following: o Change in PROMIS Sleep-related impairment short form 8a o Change in PROMIS Sleep disturbance short form 8b | Win ratio analysis described in Section 4.4.3.1 will be conducted. |
| Change in supportive secondary PROs | Summary of item 8 of PROMIS Sleep Disturbance short form 8b | Counts and percentages of participants at each time point will be summarized by nominal visit and by treatment. A shift table from baseline to postbaseline will be created at each postbaseline visit. |
| | Change in: SF-36v2 acute form domain scores From baseline to Week 52 | MMRM analysis of T-score described in Section 4.4.1.1 will be conducted. Description of T-score calculation provided in Sections 4.7.2.4 and 4.7.2.5. |

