| | Percent of participants with improved categorical shift in: PGIS-OSA Sleepiness PGIS-OSA Fatigue PGIS-OSA Snoring From baseline to Week 52 | For each question, the proportion of participants with improvements from baseline will be summarized. Shift analysis from baseline to Week 52 will also be performed. |
| | Proportion of participants who achieve: $\leq -x$ change in PROMIS Sleep-related impairment $\leq -y$ change in PROMIS Sleep disturbance | Logistic models described in Section 4.4.1.1 with the following covariates: treatment, geographic region (US/OUS) baseline AHI (not severe/severe), gender, and baseline score as a covariate. |

| Objective – Demonstrate Superiority of Tirzepatide MTD to Placebo for: | Endpoint | Analytical Approaches |
|--|---|---|
| | From baseline to Week 52 (x and y will be derived from blinded interim analysis) | |
| Change in Insulin | Change in fasting insulin from baseline to Week 52 | MMRM analysis described in Section 4.4.1.1 will be conducted. |
| Change in DBP | Change in DBP from baseline to Week 48 | MMRM analysis described in Section 4.4.1.1 will be conducted. |

Abbreviations: AHI = Apnea-Hypopnea Index; DBP = diastolic blood pressure; ESS = Epworth Sleepiness Scale; FOSQ = Functional Outcomes of Sleep Questionnaire; HDL = high-density lipoprotein; MMRM = mixed model repeated measures; MTD = maximum tolerated dose; PGIS-OSA = Patient Global Impression of Status Obstructive Sleep Apnea; PRO = patient-reported outcome; PROMIS = Patient-Reported Outcomes Measurement Information System; SF-36v2 = Short-Form 36 version 2.

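### The logistic model for the remission endpoint omits baseline ESS, one of the two measures that define response: a small, avoidable loss of precision, not a bias

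*SAP*

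**What the plan says.** **Endpoint.** SAP 1.1 and 4.4.1 define response at Week 52 as an AHI below 5, or the second branch, "AHI 5 through 14 and ESS" of 10 or less. SAP 4.4.1 places it among the key secondary endpoints tested by a graphical procedure meant to "strongly control the overall Type 1 error (2-sided alpha level of 0.05").

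**Model.** SAP 4.4.1.1 gives one sentence and one covariate list for both AHI responder endpoints. The comparison "will be conducted using logistic regression analysis including the following terms as a covariate": treatment, region (US/OUS), baseline AHI and gender. Unconditional risk differences are to be reported as well. Protocol 9.3.3 has the same model apart from the region coding: the comparison "will be conducted using logistic regression analysis including terms for treatment, pooled country, gender, and baseline AHI as a covariate". Neither document gives a reason for leaving ESS out.

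**General rule.** SAP 4.1.1: "In addition, the baseline value of the endpoint will be used as a covariate when appropriate".

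**Other responder models.** In SAP Table GPIF.4.3 the body-weight responder models include "gender, and baseline bodyweight as a covariate", and the PROMIS responder models include "gender, and baseline score as a covariate".

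**Baseline ESS.** It is scheduled at Visit 1 (Protocol 1.3) and has its own selection rule in SAP 4.1, which begins "To select the baseline observation for PROs which are planned to be completed on the same day as the PSG (ESS, FOSQ". It is also a subgroup factor for change in AHI (SAP 4.7.3). It is not a randomisation stratum (Protocol 6.3).

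**The concern.** For any participant whose Week 52 AHI falls between 5 and 14, response is settled by ESS alone. Baseline ESS is a natural predictor of Week 52 ESS, so it carries information about response that baseline AHI does not. Every other key secondary endpoint is modelled with the baseline of the measure it is built on. This one has two defining measures and uses the baseline of one. The covariate list may simply have been shared with the endpoint of at least 50% AHI reduction, which does not involve ESS, though the documents do not say so.

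What is at stake is precision in a Type 1 error-controlled comparison, at almost no cost to recover.

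**Working it through.** **1. The plan's own power figure.** SAP 5 and Protocol 9.5 give no power for this endpoint. The nearest figure is at least 90% power for percent change in AHI: difference 50, SD 50, two-sided 0.05, 103 per arm, 25% dropout.

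- n per arm for 90% power = 2 × (1.960 + 1.282)² × (50/50)² ≈ 21.0, rounded up to 22; 22/0.75 = 29.3, so 30 with dropout.
- Completers: 103 × 0.75 ≈ 77 per arm. Power at 77 exceeds 99.99%.

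The stated lower bound therefore holds. It says nothing about remission; only the 77 per arm is carried forward.

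**2. Simulation inputs.** All of these are assumptions, because the documents supply none:

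- Baseline AHI = 15 + gamma (shape 1.4, scale 25). Median AHI reduction 10% on placebo and 35% or 55% on tirzepatide, with log-scale SD 0.6.
- Baseline ESS mean 10 or 12, SD 5, generated independently of AHI. Mean ESS change -2 on placebo and -3 on tirzepatide. Baseline-to-Week-52 correlation 0.3, 0.6 or 0.8.
- Region and gender each 30/70. Complete data. The band was coded as AHI at least 5 and below 15.

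Two logistic models were fitted to each simulated trial: the SAP's four terms, and those plus baseline ESS. The risk difference is the mean over participants of

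ψ = m1 − m0 + A(Y − m1)/π − (1 − A)(Y − m0)/(1 − π),

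where m1 and m0 are the model predictions under each arm and π is the tirzepatide share. Its SE is SD(ψ)/√N. The variance ratio is (mean SE with ESS / mean SE without)².

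**3. Results, 1,500 trials per row (power in %, without → with ESS).**

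| AHI reduction, tirzepatide | ESS mean | Corr. | Responders, tirzepatide / placebo | Share in 5–14 band | Wald power | Risk-difference power | Variance ratio |
|---|---|---|---|---|---|---|---|
| 35% | 10 | 0.3 | 17.3 / 8.3% | 16.4% | 41.1 → 42.1 | 45.6 → 46.5 | 0.983 |
| 35% | 10 | 0.6 | 17.1 / 8.5% | 16.3% | 39.8 → 40.3 | 44.1 → 45.7 | 0.969 |
| 35% | 10 | 0.8 | 17.0 / 8.4% | 16.2% | 40.1 → 41.5 | 45.9 → 46.9 | 0.956 |
| 35% | 12 | 0.3 | 14.4 / 6.6% | 16.3% | 36.3 → 37.3 | 42.3 → 43.7 | 0.980 |
| 35% | 12 | 0.6 | 14.3 / 6.6% | 16.3% | 35.0 → 36.6 | 41.6 → 43.1 | 0.955 |
| 35% | 12 | 0.8 | 14.4 / 6.6% | 16.3% | 35.7 → 37.9 | 41.9 → 45.3 | 0.931 |
| 55% | 10 | 0.3 | 30.0 / 8.4% | 22.8% | 96.1 → 96.4 | 97.0 → 97.1 | 0.986 |
| 55% | 10 | 0.6 | 29.9 / 8.3% | 22.7% | 96.5 → 96.6 | 97.4 → 97.5 | 0.969 |
| 55% | 10 | 0.8 | 30.1 / 8.4% | 22.8% | 97.1 → 97.3 | 97.7 → 97.9 | 0.952 |
| 55% | 12 | 0.3 | 25.6 / 6.8% | 22.8% | 93.0 → 92.8 | 94.5 → 94.7 | 0.982 |
| 55% | 12 | 0.6 | 25.2 / 6.6% | 22.6% | 92.4 → 93.4 | 94.5 → 95.5 | 0.955 |
| 55% | 12 | 0.8 | 25.3 / 6.6% | 22.7% | 92.7 → 93.7 | 94.2 → 95.4 | 0.927 |

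The variance falls by 1.4% to 7.3%. That equals 1/0.986 − 1 = 1.4% to 1/0.927 − 1 = 7.9% more participants. Wald power changes by -0.2 to +2.2 points; the single fall is 0.002 × 1,500 = 3 trials. Risk-difference power rises by 0.1 to 3.4 points. The gain is small because ESS matters only in the 5–14 band, which holds 16% to 23% of participants.

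**4. Level under no effect, 3,000 trials in each of two settings.** Wald: 4.7% and 4.2% without ESS, 4.9% and 4.5% with it. Risk difference: 5.7% without in both, 6.3% and 6.4% with. The simulation SE at 5% is √(0.05 × 0.95/3000) = 0.40 points, so the risk-difference test with ESS is about 3.3 to 3.5 SEs above nominal. The variance ratios compare estimated SEs (0.962 and 0.916 in these null settings), so part of the apparent gain may be an SE that is slightly too small.

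**5. Cost of a missing covariate.** If participants without a baseline ESS were dropped, the variance would grow by 1/(1 − m) for a missing fraction m. The gain is cancelled at m = 1 − ratio, that is 1.4% to 7.3%.

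**The case against.** The strongest reply is that this is a covariate preference. Protocol and SAP agree on the model. The rule in SAP 4.1.1 ends with a qualifier that leaves the choice to judgement. Because entry requires AHI of at least 15 (Protocol 5.1), essentially everyone is a non-responder at baseline, so the composite has no informative baseline of its own. The plan does include baseline AHI, which governs both branches. The body-weight and PROMIS models each concern one measure and set no precedent for a composite. Responders may also be few: 77 × (0.143 + 0.066) ≈ 16 to 77 × (0.301 + 0.084) ≈ 30, or about 3 to 6 per term with five terms.

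Most of that stands and limits the point to an inexpensive improvement. It does not explain why one defining measure is represented and the other is not.

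A reader might infer more than the documents support:

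- *That SAP 4.1.1 is breached.* Its qualifier means it is not.
- *That chance imbalance in ESS biases the result.* Randomisation prevents bias, and the standard error already allows for imbalance in an unadjusted covariate. This is the same precision point, not a second harm. The Wald test held its level without ESS.
- *That baseline ESS goes unused, or that AHI is the only adjustment.* ESS serves its own change analysis and a subgroup analysis, and this model also has region and gender.

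**Conclusion.** The point holds as a matter of precision and consistency. The model for a Type 1 error-controlled endpoint leaves out a collected baseline measure that is likely to predict response. Under the assumed inputs the loss is about 1% to 7% of the risk-difference variance and roughly 0 to 2 points of Wald power, possibly nil. The size depends on the assumed ESS distribution, ESS correlation, AHI effects and complete data. The risk-difference gain is the less certain of the two, because that test ran slightly above its nominal level, more so with ESS added. Nothing here calls the planned comparison's validity into question.

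**What to change.** Before unblinding, in SAP 4.4.1.1:

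- Add continuous baseline ESS to the logistic model and to the unconditional risk difference for the remission/mild non-symptomatic endpoint only. Leave the model for at least 50% AHI reduction as it is.
- Use only ESS recorded before the first dose as the covariate. The last fallback in SAP 4.1 accepts an observation within 7 days of treatment start, which could follow the first dose; for this model, treat such a value as missing.
- State one rule for missing baseline ESS under both estimands, for example imputation from baseline data pooled across arms. The present text does not settle this. SAP 4.4.3.1 only permits imputation of PRO baselines, SAP 4.1.2 imputes missing baselines for the treatment regimen estimand but rules out explicit imputation for the efficacy estimand, and SAP 4.7.2.3 voids an ESS total with any missing item.
- Check the small-sample level of the risk-difference variance estimator at the expected number of responders.

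**Cost.** One more term with possibly few responders, and an entry in the SAP version table. Protocol 9.3.1 requires an amendment only when a principal feature changes. The conditional odds ratio shifts slightly in meaning (mean log odds ratio 2.02 → 2.21 in the last table row); the risk difference does not. If the model can no longer change, record the reason and prespecify the ESS-adjusted model as a sensitivity analysis, which SAP 4.4.1.2 leaves room for.

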4.4.1.2. Sensitivity Analyses

For participants in ISA2, sensitivity analyses for the key secondary endpoints will be carried out: percent change in AHI, clinically meaningful change in AHI, and achieving OSA remission/mild nonsymptomatic OSA.

For percent change in AHI, the sensitivity analysis using both the treatment regimen and efficacy estimand will be carried out. When using a treatment regimen estimand approach, participants with PAP withdrawal less than 5 days before the PSG at baseline or at Week 52 will have their data censored. Censored postbaseline data will be imputed using the approach outlined in

Section 4.1.2. An ANCOVA model will be fit using the approaches outlined in Section 4.3.2. When using the efficacy estimand, observations made with a PAP withdrawal less than 5 days prior to the PSG or PROMIS from the MMRM will be censored.

For the binary endpoints of clinically meaningful change in AHI and achievement of OSA remission/mild nonsymptomatic OSA, the sensitivity analysis using both estimands will be carried out. PSG measurements taken after <5 days of PAP withdrawal will be censored. After censoring, analysis will be carried out as described in Section 4.4.1.1.

Additional sensitivity analyses for ISA2 participants to accommodate participants with PAP withdrawal <5 days prior to the PSG or PROMIS or ESS may be considered.

A 2-way tipping point analysis may also be utilized for the primary endpoint. This analysis will begin with the primary analysis aligned to the treatment regimen estimand and then adding positive and negative penalties simultaneously to both the tirzepatide MTD arm and the placebo arm, considering when results tip from superiority to inconclusive, and then considering the clinical plausibility of such scenarios.

Additional sensitivity analyses for both ISAs may be included as needed.

4.4.2. Type 1 Error Rate Control Strategy for Primary and Key Secondary Efficacy Analyses

All primary and key secondary hypotheses will be tested with the overall family-wise Type 1 error rate at a 2-sided alpha level of 0.05 through the multiplicity control approach based on the graphical multiple testing procedure. The primary endpoint hypothesis will be tested at a 2-sided alpha level of 0.05 for statistical significance. If the primary efficacy endpoint is significant, the alpha of 0.05 will be propagated to the key secondary efficacy endpoints. The detailed graphical testing scheme is outlined in Figure GPIF.2.1.

The analyses will be performed for both the treatment regimen and efficacy estimands described in Section 4.3 using the same graphical testing scheme. An overall 2-sided alpha of 0.05 to control Type 1 error rate separately for the treatment regimen estimand and the efficacy estimand will be used.

